3.1.2.1 Time to response (TTR)

TTR will be used in support to the DOR endpoint and will be assessed in the response evaluable analysis set (patients who are retreated with durvalumab in Cohort 2).

TTR is defined as the time from the date of first retreatment dose until the date of first documented response (CR or PR), which is subsequently confirmed.

TTR will be calculated as follows: date of documented response (CR or PR) – date of first retreatment dose +1. The date of first documented response will coincide with that used for the DOR endpoint. TTR will be expressed in months.

TTR will not be defined for those patients who do not have a documented response (CR/PR) that is subsequently confirmed.

3.1.3 Overall survival (OS)

OS will be assessed in the FAS.

OS is defined as the time from the date of randomization/date of first dose in the parent clinical study until death due to any cause. For randomized parent studies, the randomization date will be used in the calculation of OS. For single-arm parent studies (durvalumab monotherapy) and combination parent studies, the date of first dose (durvalumab or combination treatment) will be used in the calculation of OS.

Any patient not known to have died at the time of analysis will be censored based on the last recorded date on which the patient was known to be alive (Date subject confirmed to be alive (SUR_DAT), recorded within the SURVIVE module of the eCRF).

Patient contact calls to determine survival will be made within 7 days following the date of DCO for the OS analysis, and if patients are confirmed to be alive or if the death date is after the DCO date these patients will be censored at the date of DCO. The status of ongoing, withdrawn (from the study) and “lost to follow-up” patients at the time of the final OS analysis should be obtained by the site personnel by checking the patient’s notes, hospital records, contacting the patient’s general practitioner and checking publicly available death registries. In the event that the patient has actively withdrawn consent to the processing of their personal data, the vital status of the patient can be obtained by site personnel from publicly available resources where it is possible to do so under applicable local laws.

Note that when a survival sweep is performed the SURVIVE module should be completed for every patient.

Note, for any OS analysis performed prior to the final OS analysis, in the absence of survival calls being made, it may be necessary to use all relevant case report forms (CRF) fields to determine the last recorded date on which the patient was known to be alive for those patients still on treatment (since the SURVIVE module is only completed for patients off treatment if a survival sweep is not performed). The last date for each individual patient is defined as the latest among the following dates recorded on the CRFs:

- AE start and stop dates
- Admission and discharge dates of hospitalization

- Study treatment date
- End of treatment date
- Laboratory test dates
- Date of vital signs
- Disease assessment dates on RECIST CRF
- Start and stop dates of alternative anticancer treatment
- Date last known alive on survival status CRF
- End of study date

Note that for the final analysis, the SUR_DAT date defined earlier in this section should be used as censoring date for every patient. For the final analysis, the list of above CRF dates should not be used to determine the censoring date.

If a patient is known to have died where only a partial death date is available, then the date of death will be imputed as the latest of the last date known to be alive +1 from the database and the death date using the available information provided and the rules for imputing AE start dates (section 3.2.1).

If there is evidence of death but the date is entirely missing, it will be treated as missing, i.e., censored at the last known alive date +1.

Survival status will be assessed using “SURVIVE” module of the eCRF, where the following information will be collected:

- Subject status:
 - Dead
 - Alive
 - Lost to follow-up
 - Unknown
- Date subject confirmed to be alive
- Contact date

If death occurs, the following details on death will be recorded in “DEATH” module of the eCRF:

- Date of death
- Autopsy performed (yes/no)
- Cause of death (primary and secondary)

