7.2 Lost to follow-up

Patients will be considered lost to follow-up only if no contact has been established after 2 consecutive failed contacts. A “contact” is defined as 3 attempts of the preferred method of contact recorded in the patient contact module, and then 3 attempts of the preferred alternative contact designee ± 2 weeks from the targeted date (set by the interval shown in the SoAs). At this time, the patient will be flagged as lost to follow-up in the electronic data capture (EDC; 2 consecutive time points with no patient or alternative contact), whereby the Investigator would be requested to review the patient record and update the patient status, if known. Patients who refuse to continue participation in the study, including telephone contact (or a prespecified preferred method of contact, as an alternative), should be documented as “withdrawal of consent” rather than “lost to follow-up.” Investigators should document attempts to re-establish contact with missing patients throughout the study period. If contact with a missing patient is re-established, the patient should not be considered lost to follow-up and evaluations should resume according to the protocol.

In order to support key endpoints of OS analyses, the survival status of all patients in the full analysis and the safety analysis sets should be re-checked, this includes those patients who withdrew consent or are classified as “lost to follow-up.”

- Lost to follow-up – site personnel should check hospital records, the patients’ current physician, and a publicly available death registry (if available) to obtain a current survival status. (The applicable CRF modules will be updated.)
- In the event that the patient has actively withdrawn consent to the processing of their personal data, the survival status of the patient can be obtained by site personnel from publicly available death registries (if available) where it is possible to do so under applicable local laws to obtain a current survival status. (The applicable CRF modules will be updated.)

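### SAP 3.1.3 gives two conflicting censoring dates for the final overall survival analysis: the data cut-off, and SUR_DAT for every patient with no cap at the cut-off

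*SAP*

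**What the plan says.** All the censoring rules are in SAP 3.1.3.

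- **General rule.** A patient not known to be dead "will be censored based on the last recorded date on which the patient was known to be alive". That date is SUR_DAT, the confirmed-alive date in the SURVIVE module.
- **Calls after the cut-off.** "Patient contact calls to determine survival will be made within 7 days following the date of DCO for the OS analysis". If patients are confirmed alive, "or if the death date is after the DCO date these patients will be censored at the date of DCO".
- **Final analysis.** "the SUR_DAT date defined earlier in this section should be used as censoring date for every patient". The listed CRF dates may not be used to set the censoring date.
- **Analyses before the final one.** Where no calls are made, it may be necessary to take the latest of ten CRF items for patients still on treatment, "since the SURVIVE module is only completed for patients off treatment if a survival sweep is not performed". The items include the last-alive date from the survival status form and "End of study date", which the section does not define.
- **Sweep.** When a survival sweep is done, SURVIVE should be completed for every patient. At the final analysis, sites should obtain the status of ongoing, withdrawn and lost patients from notes, hospital records, the general practitioner and death registries.

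Protocol 8.2.2 sets survival contacts every 3 months (±2 weeks), starting 90 days after the last dose, plus a contact generally within 7 days of the DCO for patients on treatment or in survival follow-up. SAP 5.2.1 plans overall survival as a listing. Integrated Kaplan-Meier, log-rank or Cox analyses are done only as needed.

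**The concern.** Two sentences cover the same patients at the same analysis and give different dates. After a sweep call SUR_DAT falls on or after the DCO, so a programmer must choose between the DCO and the call date.

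Under the SUR_DAT sentence, follow-up runs past the DCO for patients found alive, while deaths after the DCO are still treated as censored at the DCO. That extra time cannot contain an event. For a patient found to have died after the DCO, the most recent SUR_DAT may be a routine contact well before the DCO, although the patient is known to have been alive at the DCO.

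The bar on other dates has two further problems. The barred list contains the last-alive date from the survival status form, which appears to be SUR_DAT itself. And if a patient on treatment has no SUR_DAT despite the sweep, the SAP gives no substitute, even where dosing or laboratory dates show the patient was alive.

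At stake are the censoring dates and survival times in the listing, and any integrated time-to-event analysis that reuses the derivation.

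**Working it through.** The SAP gives no figure here to reproduce: no event count, power or test is stated for overall survival. The check compares the two rules and then bounds the difference.

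**Inputs from the documents.** Calls 0 to 7 days after the DCO (SAP 3.1.3); contacts every 3 months ±2 weeks (Protocol 8.2.2); about 600 patients (SAP 1.3).

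**The rules side by side**, with the call on day DCO + k, k = 0 to 7:

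| Patient | DCO rule | SUR_DAT rule, read literally | Difference |
|---|---|---|---|
| Confirmed alive at the call | DCO | DCO + k | 0 to 7 days later |
| Died after the DCO, before the call | DCO | Last confirmed-alive date | Up to about 119 days earlier |
| On treatment, no SUR_DAT despite the sweep | Not covered | No date available | Undefined |

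**Bounds.**

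- Confirmed alive: 7 / 30.44 = 0.23 months per patient at most. If all 600 were alive: 600 × 7 / 365.25 = 11.5 patient-years.
- Death between the DCO and the call: one contact 2 weeks early and the next 2 weeks late gives 91.3 + 14 + 14 = 119.3 days. This assumes a patient in survival follow-up with no missed contact.
- Number of such deaths: assume a 2-year (730-day) median with a constant hazard, 0.693 / 730 = 0.00095 per day. With all 600 alive at the DCO and an average wait of 3.5 days, 600 × 0.00095 × 3.5 = about 2 patients.

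**Simulation on assumed inputs.** 200 runs of 600 patients; entry spread evenly over 3 years; DCO at 5 years; exponential survival with median 2, 4 or 6 years; calls 0 to 7 days after the DCO; last earlier contact 0 to 119 days before it. The table gives the largest absolute change from the DCO rule in any run.

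| Assumed median | Rule | 24-month survival | 36-month survival | Kaplan-Meier median |
|---|---|---|---|---|
| 2 years | SUR_DAT, no cap | 0.0002 | 0.0008 | 3 days |
| 2 years | Earlier of SUR_DAT and DCO | 0.0002 | 0.0004 | 3 days |
| 4 years | SUR_DAT, no cap | 0.0001 | 0.0006 | 111 days |
| 4 years | Earlier of SUR_DAT and DCO | 0.0001 | 0.0001 | 22 days |
| 6 years | SUR_DAT, no cap | 0.0001 | 0.0006 | 36 days |
| 6 years | Earlier of SUR_DAT and DCO | 0.0001 | 0.0001 | 0 days |

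The larger shifts in the median are single-run maxima, where the median falls in the sparse tail of the curve or is reached in few runs. A cap alone leaves a small difference, because patients who die between the DCO and the call are still censored at their last contact. Censoring those patients at the DCO as well, as proposed below, reproduces the DCO rule exactly in this set-up.

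**The case against.** The best defence is that the two sentences are meant to be read together. The final-analysis note contrasts SUR_DAT with the CRF list as a data source and refers back to the paragraph that holds the DCO rule. The natural combined reading is SUR_DAT truncated at the DCO, and relying on a complete sweep at the final analysis is a deliberate and reasonable choice. That reading is probably what was intended. It stands as an argument for low severity, but not as a resolution: no sentence states the cap, the note says every patient, and a cap alone does not settle deaths between the DCO and the call.

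The defence is also right about two stronger readings that a reader might infer.

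- **That a patient on treatment could lose the whole WAVE treatment period.** This needs a patient seen every 4 weeks to escape the all-patient sweep, the Protocol 8.2.2 contact and the site record checks. That would be a failure of conduct. The plan lacks a fallback for it, but nothing in the documents suggests it is likely.
- **That the SAP accepts an administrative date as proof of life and so adds 3 to 6 months for lost patients.** Under Protocol 7.2, "Patients will be considered lost to follow-up only if no contact has been established after 2 consecutive failed contacts", and those 3-monthly contacts concern patients off treatment. The fallback list is introduced for patients still on treatment, only before the final analysis and only without calls. Patients off treatment have the SURVIVE module. The SAP does not define "End of study date", so calling it administrative is conjecture. Whether any pre-final analysis takes place is also unsettled: SAP 6 plans no interim analysis, while Protocol 9.4 plans five.

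What remains of the second reading is loose drafting. The list also holds items that arise after treatment ends, and an undefined end date is not in itself evidence that a patient was alive.

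**Conclusion.** The conflict is real and the text is wrong as written, but the consequence is minor. For patients confirmed alive the two rules differ by 0 to 7 days. For the few who die between the DCO and the call, the censoring date may move back by up to about 119 days, assuming routine contacts are kept. Survival at 24 and 36 months changed by at most 0.0008 in simulation. The median was sensitive only where the data were sparse, and these results rest on the assumed survival, entry and contact patterns.

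The planned output is a listing and nothing is tested, so no conclusion of the study turns on this. The point matters for the reproducibility of the listed dates and for any integrated time-to-event analysis. The documents do not support a claim of months of unobserved survival or of lost treatment periods.

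**What to change.** Replace the final-analysis sentences in SAP 3.1.3 with one rule:

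1. Patients confirmed alive on or after the DCO, and patients who die after the DCO, are censored at the DCO.
2. All other patients not known to have died are censored at the last SUR_DAT on or before the DCO.
3. Only if SUR_DAT is missing, or earlier than other direct evidence of life (a dose, visit, laboratory, vital-sign or scan date), use that later date, capped at the DCO.

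Remove the survival-form alive date from the barred list, or state how it differs from SUR_DAT. In the pre-final fallback list, define "End of study date" and count it only when it coincides with a documented contact.

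The cost is a few lines of SAP text and a standard derivation. No new data are needed, and the sweep stays the main source at the final analysis.

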3.2 Safety variables

Safety and tolerability will be assessed in terms of AEs (including SAEs), deaths, laboratory data, vital signs, and exposure (i.e., durvalumab monotherapy or combination therapy). These will be collected for all patients. The following safety variables will be assessed:

- All SAEs
- Non-serious AEs that lead to dose modification, drug discontinuation, or withdrawal from the study
- All Grade 3 and Grade 4 AEs
- Grade 2 AEs that affect vital organs (e.g., heart, liver, kidney, lungs, central nervous system)
- Immune-mediated AEs
- Laboratory findings qualifying as an SAE/AE (endpoints defined above) up until 90 days after the last dose of durvalumab in all patients

3.2.1 Adverse events

“On treatment” will be defined as assessments between date of start dose and 90 days following discontinuation of Investigational Product (IP) (i.e., the last dose of durvalumab in combination with any other approved or investigational anticancer agents or durvalumab monotherapy). For AEs, on treatment (or treatment-emergent AEs) will be defined as any AEs that started after dosing or prior to dosing and which worsens following exposure to the treatment. The Medical Dictionary for Regulatory Activities (MedDRA) (using the latest or current MedDRA version) will be used to code the AEs. AEs will be graded according to the National Cancer Institute Common Terminology Criteria for AEs (using the CTCAE version 5).

AEs will be assessed using the following eCRF modules:

Adverse Events (AE)

- Adverse Event (y/n)
- AE medical code
- Date AE started
- Date AE stopped
- Serious AE (y/n)
- Action taken with durvalumab (Dose not changed; Drug Interrupted; Drug permanently discontinued; Not applicable)
- AE outcome (Recovered/resolved; Recovering/resolving; Recovered/resolved with; sequelae, Not recovered/not resolved; Fatal)
- Reasonable Possibility AE Caused by durvalumab (y/n)

- CTCAE Grade (Mild AE; Moderate AE; Severe AE; Life-threatening or disabling AE; Death related to AE)
- Dose Limiting Toxicity (y/n)
- Immune-mediated AE (y/n)
- Infusion Reaction AE (y/n)

Serious Adverse Event Report (SERAE)

- AE medical code
- Date AE met criteria for serious AE
- Date investigator aware of serious AE
- AE is serious due to (medical code)
- Death (y/n)
- Inpatient hospitalization or prolongation of existing inpatient hospitalization (y/n)
- Congenital anomaly or birth defect (y/n)
- Life-threatening (y/n)
- Persistent or significant disability/incapacity (y/n)
- Important medical event (y/n)
- Date of hospitalization
- Date of discharge
- SAE caused by other medication (y/n)
- SAE caused by study procedure(s) (y/n)
- Description of AE

AE of Special Interest (AESI)

- AE medical code
- AE SI (full list of AESI is reported in the Appendix section)
- Current Bowel Movements CTCAE Grade (Mild AE, Moderate AE, Severe AE, Life-threatening or Disabling AE, Death Related to AE)
- Body Surface Area Covered (<10%, 10-30%, >30%)
- Anatomical Site [up to 6 sites] (Lower Leg, Other, Abdominal Cavity, Inguinal Region, Back, Neck, Face, Chest, Arm, Foot, Hand, Buttock, Scalp)
- Signs and Symptoms (Abdominal Pain, Paresthesia, Loss of Deep Tendon Reflexes, Rapid Progressive Weakness, Respiratory Insufficiency, etc.)

- Specialist Consulted or Additional Inv (y/n)
- Services and Result Description
- Any Additional Laboratory Investigations (y/n)
- Any Significant Medic or Surgical History (y/n)
- Event Triggered by Disease Progression (y/n)
- Event Attributed to Disease/Metastasis (y/n)
- Anatomic Location
- Potential Alternate Etiology (y/n)

In addition to the above modules, AEs can be detected based on examinations and tests (physical examinations, vital signs and laboratory tests; these are described in Sections 3.2.2, 3.2.3, and 3.2.4 respectively). Situations in which examinations and tests results should be reported as AEs are described in Section 8.3.7 of the CSP.

AE imputation rules

For missing AE start dates, the following imputation rules will be applied

- If the day is missing, the 1st day of the month will be used unless month is the same as month of the first dose of study drug then the first dose date will be used.
- If the day and month are missing, 1st January will be used unless year is the same as first dose date then the first dose date will be used.
- Completely missing-impute first dose date unless the end date suggests it could have started prior to this in which case impute the 1st January of the same year as the end date.

For missing AE end dates, the following imputation rules will be applied:

- If the day is missing, the last day of the month will be used unless month is the same as month of study discontinuation, then impute as study discontinuation date.
- If the day and month is missing, the 31st December will be used unless year is the same as year of study discontinuation then impute study discontinuation date.

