8.3.2 Time period and frequency for collecting AE and SAE information

AEs and SAEs will be collected from the time of the patient signing the ICF until the follow-up period is completed (90 days after the last dose of durvalumab). If an event that starts post the defined safety follow-up period noted above is considered to be due to a late onset toxicity to study drug, then it should be reported as an AE or SAE as applicable. Collection and reporting of AEs and SAEs after the final DCO is described in Section [8.3.14](#).

All SAEs will be recorded and reported to the Sponsor or designee within 24 hours, as indicated in [Appendix A](#). The Investigator will submit any updated SAE data to the Sponsor within 24 hours of it being available.

Investigators are not obligated to actively seek AE or SAE in former study patients. However, if the Investigator learns of any SAE, including a death, at any time after a patient's last visit and he/she considers the event to be reasonably related to the study treatment or study participation, the Investigator should notify the Sponsor.

The method of recording, evaluating, and assessing causality of AE and SAE and the procedures for completing and transmitting SAE reports are provided in [Appendix A](#).

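### Partial AE start dates are set to the first-dose date without a stop-date check, so an event that ended before the first WAVE dose gets an onset after its own end

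*SAP*

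**What the plan says.** SAP 3.2.1 (AE imputation rules) has three rules for AE start dates:

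- **Day missing:** the 1st of the month, "unless month is the same as month of the first dose of study drug then the first dose date will be used".
- **Day and month missing:** "1st January will be used unless year is the same as first dose date then the first dose date will be used".
- **Completely missing:** "impute first dose date unless the end date suggests it could have started prior to this". In that case the rule uses 1 January of the year of the end date.

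Only the third rule refers to the end date. The same section counts as treatment-emergent "any AEs that started after dosing or prior to dosing and which worsens following exposure to the treatment", and it opens the on-treatment window on the date of the starting dose.

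Protocol 8.3.2 states that "AEs and SAEs will be collected from the time of the patient signing the ICF", so collection can begin before any dose in this study. The AE stop date is a field of the AE eCRF module (SAP 3.2.1).

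**The concern.** Imputing the first-dose date is a sensible cautious choice when nothing shows whether an event began before or after dosing. It fails when a recorded stop date shows that the event was over before the dose. The SAP guards against this when the start is wholly unknown, but not when the month or year is known. A record with more information is therefore handled worse than one with less.

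The situation can occur in two cohorts. Cohort 1 patients consent before Day 1, and their baseline may take more than one visit (Protocol Table 1, footnote b). Cohort 2 patients sign the follow-up consent while off treatment and may be retreated much later (Protocol Table 2, footnotes d and e), which brings the year-level rule into play. Safety events ongoing at the end of the parent study are also carried in (Protocol 8.2.1; SAP Table 2), and these may resolve before the first dose here.

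At stake is the onset of these events relative to WAVE dosing. That onset decides whether an event is read as starting on continued treatment or retreatment, and it underlies the by-cohort AE summaries that serve the primary safety objective (SAP 2.1.3 and 5.2.5). SAP 5.2.5 also lists the dose at the time of each AE. If that is derived from the onset date, it would show a WAVE dose for an event that preceded it.

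**Working it through.** The plan gives no figure to reproduce. The check applies the three rules as written to constructed dates, which are assumptions and not trial data.

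**Rule as written.** If the known part of the start (month and year, or year alone) matches the first dose, start = first-dose date. Otherwise, start = the 1st of the month or 1 January. A completely missing start becomes the first-dose date, or 1 January of the stop year if the stop precedes the dose.

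**Rule with the check added.** As above, but if the stop precedes the first dose, the partial-date rules keep the 1st of the month or 1 January.

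**Duration** = stop - start + 1, in days. An imputed start on or after the first-dose date is taken as treatment-emergent.

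| Case | Start recorded | Stop | First WAVE dose | Start as written | Duration | Start with check | Duration |
|---|---|---|---|---|---|---|---|
| A | Mar 2020, no day | 12 Mar 2020 | 20 Mar 2020 | 20 Mar 2020 | 12 - 20 + 1 = -7 | 1 Mar 2020 | 12 |
| B | 2020 only | 31 Mar 2020 | 16 Nov 2020 | 16 Nov 2020 | -230 + 1 = -229 | 1 Jan 2020 | 91 |
| C | Completely missing | 31 Mar 2020 | 16 Nov 2020 | 1 Jan 2020 | 91 | 1 Jan 2020 | 91 |
| D | Mar 2020, no day | 2 Apr 2020 | 20 Mar 2020 | 20 Mar 2020 | 14 | 20 Mar 2020 | 14 |

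- A and B get an onset after their own stop and are classed as treatment-emergent. With the check, neither is.
- B and C differ only in that B's year of onset is known. C, with less information, gets a possible date; B does not.
- D shows that a record whose stop falls after the dose does not change.
- In a 31-day month there are 31 x 30 / 2 = 465 pairs with a stop day before the first-dose day. All 465 give an impossible onset when only the start day is missing. This shows that the rule has no exception; it says nothing about how often such records occur.

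**Limits of the trigger.** The partial start must share the month or year with the first dose, and the stop must precede that dose. A stop with only its day missing in the first-dose month raises no conflict in general, because SAP 3.2.1 imputes it to month end or to study discontinuation.

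**Which first dose is meant.** The bullets do not say whether the reference dose is in the parent study or in this one. The protocol uses the same term for the dose in this study in Table 1, footnote i (pregnancy testing) and, expressly, in exclusion criterion 11 (live vaccines). SAP Table 2 transfers the parent first-dose date only for non-randomized parent studies, so a parent-dose reference would not be available from that transfer for the others.

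**The case against.** The strongest reply is that the consequence is limited, and most of that reply stands.

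- A reader might infer that events which ended before any durvalumab exposure enter the tables. The documents do not support this. Every patient received durvalumab in a parent study (inclusion criterion 2), and Cohort 1 is on durvalumab at entry (criterion 5).
- The safety set includes patients enrolled within 90 days of a parent dose (SAP 2.1.3). Patients more than 90 days past their last dose have no routine AE follow-up (Protocol Table 2, footnote a). Many pre-dose AEs therefore fall in the post-dose window of the parent study and may be tabulated whatever their imputed start. Case B could well be such an event.
- A reader might also infer that the primary endpoint is treatment-emergent AEs as such. It is a list of AE categories (SAP 1.1) without that qualifier.
- Negative durations distort no planned result, because no analysis of AE duration is specified.
- The study tests no hypothesis, and the rule errs towards counting events as on treatment, so it does not hide a signal.

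Three replies do not remove the point. Reading the reference dose as the parent dose would make the conflict disappear, but the protocol's usage and SAP Table 2 point the other way. The eCRF edit checks (Protocol 11.1.5) may reduce partial dates, but they act on entered data and not on later imputed values. The phrase on events starting after dosing is ambiguous for an event dated on the dosing day, but the on-treatment window opens on that day, and the onset is impossible either way.

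**Conclusion.** The point holds as a certain but narrow error of logic. As written, any AE with a partial start in the month or year of the first WAVE dose and a stop before that dose gets an onset after its own end and is classed as starting on WAVE treatment or retreatment. Nothing elsewhere in the SAP or protocol overrides this.

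The number of such records is not derivable and is probably small. The documents do not support a claim that the safety tables are materially inflated. Some of these events belong in the tables through their parent-study exposure; for those, the error is in the onset and in the attribution to WAVE dosing.

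The conclusion rests on two readings: that the reference dose is the first dose in this study, and that an onset on the first-dose date counts as on treatment. Cohort 3 and Cohort 2 patients who are never retreated have no dose in this study, so the conflict does not arise for them.

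**What to change.** In SAP 3.2.1:

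1. In both partial-date bullets, use the first-dose date only if the stop date is missing or on/after the first dose. Otherwise use the 1st of the month or 1 January.
2. State that an imputed start may never be later than the stop date.
3. State that the reference dose is the first dose in this study, and say what the completely missing rule does for patients who have no such dose.

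The main change costs one sentence in the SAP and one condition in the derivation program. It needs no new data, since the stop date is already collected. Records with a missing stop date, or a stop on/after the first dose, do not change. SAP 3.1.3 borrows these rules for partial death dates; a death has no stop date, so the added condition leaves those imputations as they are.
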